2.6 Analysis of the key secondary objective

There is no key secondary objective defined in the protocol.

2.7 Analysis of secondary efficacy objective(s)

2.7.1 Secondary endpoints

No multiplicity adjustment will be carried out for secondary analyses described below. In addition, the treatment effect of QBW251 compared to placebo that would have been observed had all patients remained on their assigned treatment will be estimated. Only on-treatment data will be used.

All analysis of secondary endpoints will be performed on the FAS.

Missing data for any reason will not be explicitly imputed and will be handled by the respective mixed effects model which implicitly imputes missing data assuming MAR.

If not stated otherwise, in the 450mg dose will be excluded from all inferential statistics. Descriptive analyses will include all doses.

Details on statistical models are provided in [Section 5.7](#).

2.7.1.1 COPD symptoms

2.7.1.1.1 Respiratory symptoms from E-RS

The E-RS assesses both overall daily respiratory COPD symptoms (Total score) and specific respiratory symptoms using 3 subscales (Breathlessness, Cough & Sputum, and Chest Symptoms). Higher scores indicate more severe symptoms. Details on derivation of scores and handling of missing data are provided in [Section 5.6](#).

The mean baseline E-RS Total and subscale scores will be the average of the corresponding daily scores from the run-in period. The last 14 days of the run-in period, i.e. the scheduled duration of run-in period, will be considered.

The daily scores post-randomization will be averaged for each week (Week 1, Week 2, etc.).

Monthly means over a 4-week period will also be calculated.

E-RS Cough & Sputum score

The change from baseline in the E-RS Week 12 Cough & Sputum mean scores will be analyzed using the same MCP-Mod approach described in for the primary variable in [Section 2.5](#). The change from baseline in the E-RS Cough & Sputum weekly mean scores will be analyzed using a similar MMRM as described in [Section 2.5](#) for the primary variable, with the appropriate baseline score replacing the baseline FEV₁ value in the model. The estimated treatment difference (QBW251 – placebo) at each week will be reported along with the associated 90% confidence interval. Results from MCP-Mod will be presented as described for primary variable in [Section 2.5](#).

The proportion of patients who achieve a clinically important improvement (decrease) of at least 0.7 ([Leidy et al 2014b](#)) in the weekly mean score will be analyzed using a repeated measurements logistic regression. The model will include the same terms as for the MMRM analysis of the weekly scores. The estimated odds ratios will be displayed over time along with the associated 90% confidence intervals for treatment comparison of each dose versus Placebo.

The change from baseline in the monthly mean scores will be analyzed using a similar MMRM as described for weekly scores. The proportion of patients who achieve a clinically important improvement (decrease) in the monthly mean score will also be analyzed as described for weekly scores.

E-RS Cough & Sputum weekly mean and monthly mean scores will be summarized descriptively.

E-RS Total, Breathlessness, and Chest Symptoms scores

The change from baseline in the E-RS weekly mean Total, Breathlessness, and Chest Symptom scores will be analyzed using a similar MMRM as described in [Section 2.5](#) for the primary variable with the appropriate baseline E-RS score replacing the baseline FEV₁ value. The estimated treatment difference (QBW251 – placebo) will be reported along with the associated 90% confidence interval.

E-RS mean weekly total score will be analyzed in addition using MCP-Mod as described for primary endpoint.

The minimum clinically important improvements (decrease) for the scores are defined below ([Leidy et al 2014b](#)).

- Total ≥ 2.0
- Breathlessness ≥ 1.0
- Chest Symptoms ≥ 0.70

The proportion of patients who achieve a clinically important improvement in the weekly mean scores will be analyzed using a repeated measurements logistic regression. The model will include the same terms as for the MMRM analysis of the weekly mean scores. The estimated odds ratios will be displayed over time along with the associated 90% confidence intervals for treatment comparison of each dose versus Placebo.

The change from baseline in the monthly mean scores will be analyzed using a similar MMRM as described above. The proportion of patients who achieve a clinically important improvement (decrease) in the monthly mean score will also be analyzed as described above.

E-RS Total, Breathlessness, and Chest Symptom weekly mean and monthly mean scores will be summarized descriptively.

2.7.1.1.2 Cough and sputum symptoms from CASA-Q

CASA-Q assesses cough and sputum symptoms and their impact with 4 domain scores (cough symptoms, cough impact, sputum symptoms, and sputum impact). Details on derivation of scores and handling of missing data are provided in [Section 5.6](#).

The change from baseline in the domain scores will be analyzed using the MMRM described in [Section 2.5](#) for the primary variable with the appropriate baseline domain score replacing the baseline FEV₁ value in the model. The estimated treatment difference (QBW251 – placebo) at each visit will be reported along with the associated 90% confidence interval.

CASA-Q domain scores will be summarized descriptively by visit.

2.7.1.1.3 Severity of symptoms from PGI-S

The PGI-S rates the severity of the respiratory symptoms and of cough and mucus. Shift tables will be used to compare baseline to Weeks 12 and 24 for each PGI-S value.

The PGI-S change from baseline will be analyzed using a proportional odds model for repeated measures with the same terms as for the MMRM analysis described in [Section 2.5](#) for the primary variable with the baseline PGI-S value replacing the baseline FEV₁ value. The estimated odds ratios will be displayed over time along with the associated 90% confidence intervals. For the proportional odds analysis, the change in severity scores will first be grouped into the categories below, for cough and mucus categories -5 and 5 will be added. Further groupings of the change categories (such as better, no change, and worse) may be performed prior to the proportional odds analysis, if the sample size for some of the categories are too small.

Change from baseline in severity score	Change category
-4	Very much better
-3	Much better
-2	Better
-1	Slightly better
0	No change
1	Slightly worse
2	Worse
3	Much worse
4	Very much worse

2.7.1.2 Health-related quality of life from SGRQ

SGRQ measures health impairment. A total score is produced, along with the domain scores of symptoms, activity, and impacts. Details on derivation of scores and handling of missing data are provided in [Section 5.6](#).

The Weeks 12 and 24 change from baseline in the SGRQ total and domain scores will be analyzed using the MMRM described in [Section 2.5](#) for the primary variable with the appropriate baseline SGRQ score replacing the baseline FEV₁ value in the model. The estimated treatment difference (QBW251 – placebo) at each visit will be reported along with the associated 90% confidence interval.

The proportion of patients who achieve a clinically important improvement (decrease) of at least 4 in the total score will be analyzed using a repeated measurements logistic regression. The model will include the same terms as for the MMRM analysis of the total scores. The estimated odds ratios will be displayed over time along with the associated 90% confidence intervals.

SGRQ total and domain scores will be summarized descriptively by visit.

2.8.1 Adverse events (AEs)

The on-treatment period for adverse events lasts from the date of first administration of double-blind study treatment to 30 days after the date of the last actual administration of double-blind

study treatment. Adverse events will be summarized by treatment group. Summary tables for AEs will summarize only on-treatment events (also known as treatment-emergent AEs).

The number (and percentage) of subjects with treatment-emergent adverse events will be summarized in the following ways:

- by treatment and preferred term (PT).
- by treatment, primary system organ class (SOC) and PT.
- by treatment, SOC, PT and maximum severity.

Separate summaries by SOC and PT will be provided for:

- AEs suspected to be study medication related
- fatal AEs
- leading to treatment discontinuation
- leading to dose interruptions and/or adjustments
- serious adverse events (SAEs)

Further SAEs will be summarized by PT.

In addition, treatment emergent AEs and SAEs will be presented by treatment, system organ class and preferred term, showing exposure adjusted event rates (i.e., the number of events expressed in rates per 100 patient years).

Unless otherwise specified, SOCs will be sorted alphabetically and, within each SOC, the PTs will be sorted in descending order of frequency in the highest QBW251 dose. A subject with multiple adverse events within a SOC or PT is only counted once towards the total of the SOC or PT.

Listings will be provided for all AEs, SAEs and fatal AEs.

2.8.1.1 AE reporting for CT.gov and EudraCT

For the legal requirements of clinicaltrials.gov and EudraCT, two required tables on treatment emergent adverse events which are not serious adverse events with an incidence greater than 2% and on treatment emergent serious adverse events and SAE suspected to be related to study treatment will be provided by system organ class and preferred term on the safety set population.

If for a same patient, several consecutive AEs (irrespective of study treatment causality, seriousness and severity) occurred with the same SOC and PT:

- a single occurrence will be counted if there is ≤ 1 day gap between the end date of the preceding AE and the start date of the consecutive AE
- more than one occurrence will be counted if there is > 1 day gap between the end date of the preceding AE and the start date of the consecutive AE

For occurrence, the presence of at least one SAE / SAE suspected to be related to study treatment / non SAE has to be checked in a block e.g., among AE's in a ≤ 1 day gap block, if at least one SAE is occurring, then one occurrence is calculated for that SAE.

The number of deaths resulting from SAEs suspected to be related to study treatment and SAEs irrespective of study treatment relationship will be provided by SOC and PT.

2.8.1.2 Adverse events of special interest / grouping of AEs

The number and percentage of patients who reported treatment-emergent adverse events of special interest will be summarized by risk name, PT and treatment group.

Risk names will be sorted alphabetically and, within each risk name, the PTs will be sorted in descending order of frequency in the highest QBW251 dose. If a patient reported more than one adverse event with the same PT, the AE will be counted only once. If a patient reported more than one AE within the same risk, the patient will be counted only once at that risk.

The Compound Case Retrieval Strategy (CRS) will be used to determine the MedDRA search criteria to be used to identify events of special interest. The most recent list of adverse events of special interest at the time of database lock will be used.

SAEs of special interest will be summarized by risk name, PT and treatment group.

2.8.2 In addition, treatment emergent AEs of special interest will be presented by treatment and risk, showing exposure adjusted event rates (i.e., the number of events expressed in rates per 100 patient years).Deaths

Fatal AEs will be summarized and listed as specified in [Section 2.8.1](#).

2.8.3 Laboratory data

Summaries of laboratory data will include on-treatment measurements, which are defined as measurements taken post-baseline but no later than 30 days after last dose of double-blind treatment.

Absolute values and change from baseline will be summarized for continuous laboratory parameters by visit, including the worst on-treatment value. The direction of interest for worst on-treatment value for selected hematology and biochemistry parameters is shown in [Section 5.4](#).

For selected laboratory tests, the number and percentage of patients with newly occurring or worsening laboratory abnormalities meeting the clinically notable criteria at any time on-treatment, considering all on-treatment data from scheduled, unscheduled and premature discontinuation visits, will be summarized by laboratory parameter. Notable criteria are defined in [Section 5.4](#).

Furthermore, the number and percentage of patients with newly occurring or worsening abnormalities in liver function tests (LFT) will be summarized by treatment and at any time on-treatment considering all on-treatment data from scheduled, unscheduled and premature discontinuation visit. LFT criteria are defined in [Section 5.4](#).

The baseline value is the last value prior to first dose of double-blind treatment.

For selected laboratory parameter boxplots of laboratory values relative to the normal ranges will be provided.

Laboratory data of patients with notable values will be listed. Urinalysis will be listed for patients with abnormal urine dipstick.

2.8.4 Other safety data

2.8.4.1 ECG and cardiac imaging data

Summaries of ECG data will include on-treatment measurements, which are defined as measurements taken post-baseline but no later than 30 days after last dose of double-blind treatment. Triplicate ECGs (3 ECGs are collected within about a five-minute window) will be performed. For the analysis of continuous ECG parameter the mean value of the 3 ECG measurements will be used, for ECG interpretation, all findings of the 3 ECGs will be considered.

Absolute values and change from baseline will be summarized for ECG parameters by visit and time point. The maximum on-treatment QTc value will be included in the summary.

The number and percentage of patients with newly occurring or worsening notable Fridericia's QTc values will be summarized at any time on-treatment, considering all on-treatment data from scheduled, unscheduled and premature discontinuation visits. For derivation of notable values, the mean of the triplicate ECGs will be used. Notable criteria are defined in [Section 5.5](#).

The number and percentage of patients with ECG abnormalities will be summarized by evaluation type, abnormality finding, visit and time point.

The baseline value is the last value prior to first dose of double-blind treatment.

ECG data of patients with notable Fridericia's QTc values will be listed.

2.8.4.2 Vital signs

Summaries of vital signs data will include on-treatment measurements, which are defined as measurements taken post-baseline but no later than 30 days after last dose of double-blind treatment.

Absolute values and change from baseline will be summarized for vital sign parameters by visit including the minimum and maximum on-treatment value.

The number and percentage of patients with newly occurring or worsening notable vital sign values will be summarized at any time on-treatment, considering all on-treatment data from scheduled, unscheduled and premature discontinuation visits. Notable criteria are defined in [Section 5.5](#).

The baseline value is the last value prior to first dose of double-blind treatment.

Vital sign data of patients with notable values will be listed.

2.9 Pharmacokinetic endpoints

PK measurements will be analyzed as reported; no visit windowing will be applied.

Descriptive summary statistics of QBW251B plasma concentration data will be provided by treatment and visit/sampling time point, including the frequency (n, %) of concentrations below the lower limit of quantification (LLOQ). Summary statistics will include mean (arithmetic and geometric), standard deviation, coefficient of variation (arithmetic and geometric), median, minimum and maximum. An exception to this is T_{max} where median, minimum and maximum will be presented. Concentrations below LLOQ will be treated as zero in summary statistics and for PK parameter calculations.

Pharmacokinetic parameters will be determined using non-compartmental method(s).

Summary of PK parameter of all patients in the PK set will include trough concentration C_{min} on all visits and C_{max} on Day 1, Week 2 and Week 24. Summary of PK parameter for patients in the PK serial sub-group will include C_{min} , C_{max} , AUC_{0-8h} , AUC_{0-24h} , and T_{max} on Day 1 and Week 2.

The number and percentage of patients in the PK serial sub-group above the exposure threshold of $AUC_{0-24h,ss} = 91700 \text{ ng}\times\text{h/mL}$ will be presented overall and by visit.

The number and percentage of patients in the PK set above the exposure threshold $C_{min,ss} = 2942 \text{ ng/mL}$ will be presented overall and by visit. This threshold is defined based on the exposure threshold $AUC_{0-24h,ss} = 91700 \text{ ng}\times\text{h/mL}$.

Details on derivation of exposure threshold and AUC_{0-8h} , AUC_{0-24h} are provided in [Section 5.6](#).

In addition, the plasma concentration data from this study may be combined with data from other studies to perform a population PK analysis, which will follow the principles outlined in the [FDA Guidance for Industry 1999](#). These results, if performed, will be reported outside of the CSR.

█ █

█

█ █

█

[REDACTED]

[REDACTED]

[REDACTED]

[REDACTED]

[REDACTED]

[REDACTED]

[REDACTED]

[REDACTED]

[REDACTED]

[REDACTED]

[REDACTED]

[REDACTED]

[REDACTED]

[REDACTED]

[REDACTED]

[REDACTED]

[REDACTED]

[REDACTED]

[REDACTED]

[REDACTED]

[REDACTED]

[REDACTED]

[REDACTED]

[REDACTED]

[REDACTED]

[REDACTED]

[REDACTED]

[REDACTED]

[REDACTED]

[REDACTED]

significance level across all analyses is maintained at 0.05. At each interim analysis, an exact test on the proportion of subjects who exceed the exposure threshold will be performed to test the following hypotheses for these 2 treatment arms.

- Null hypothesis (Ho): the proportion of patients exceeding the exposure threshold $< 5\%$
- Alternative hypothesis (Ha): the proportion of patients exceeding the exposure threshold $\geq 5\%$

The interim analyses are proposed to occur when approximately 20%, 40%, 60%, 80%, and 100% of subjects have completed at least 4 weeks of treatment, which should be long enough to determine if the patient's exposure will exceed the threshold or not. The corresponding stopping boundaries in the p-value scale are 0.015, 0.016, 0.017, 0.018, and 0.019 for the interim analyses. For example, when the first interim analysis is performed after 20% patients have completed 4 weeks of treatment in the 450 mg b.i.d. arm, the observed (i.e. nominal) p-value has to be equal to or smaller than 0.015 in order to reject Ho and terminate the treatment arm.

If the true proportion of patients in the 300mg or 450 mg b.i.d. treatment arm exceeding the exposure threshold is $< 5\%$, then the probability of rejecting Ho would be very low ($< 5\%$) with this group sequential test for the treatment arm. If the true proportion is 10% then the probability of rejecting Ho and stopping the treatment arm early would be high ($> 77\%$). If the timing of the actual interim analyses deviate from the proposed schedule (20%, 40%, 60%, 80%, and 100% completing at least 4 weeks of treatment), stopping boundaries will need to be recalculated using the pre-specified α -spending function and based on the actual sample size at each interim analysis. The observed p-values at the interim analyses will then be compared against the recalculated stopping boundaries.

More details will be outlined in the DMC charter and a separate DMC SAP.

After reviewing the exposure data from the first interim analysis, the DMC informed the sponsor that the 450 mg b.i.d. arm had crossed the stopping boundary and recommended termination of the treatment arm. The DMC confirmed that the arm was well tolerated in this patient population and the stop was not based on adverse reactions to the 450 mg b.i.d. regimen. The sponsor followed the DMC's recommendation and discontinued investigational treatment from all patients randomized to the 450 mg b.i.d. arm.

2.13.2 Efficacy

Up to 2 IAs on efficacy data may be conducted and the timing will correspond to 1 or 2 safety DMC analyses. The purpose of these IA(s) is to have an early assessment of the data for planning future studies in the QBW251B program. The efficacy IA results will not trigger any change or decision in the conduct of this study.

An internal Novartis committee, external to the study team, will be set up to review the both the efficacy and safety data. Once team members are exposed to the unblinded IA data, they will no longer be involved in the further execution of the study. A charter will provide further details.

The first IA will be conducted when approximately 645 to 680 patients, including the ~102 patients randomized to the 450mg b.i.d. arm, have either discontinued or completed 12 weeks of treatment. This IA will have acceptable precision for the estimated trough FEV₁ dose-

response curve. The average half-length of the 90% confidence interval is around 26 mL and 32 mL for the estimated dose-response curve and the estimated placebo-adjusted dose-response curve, respectively. If the first IA does not lead to a clear decision for the planning of the QBW251B program, a second IA may be performed when all randomized patients have either discontinued or completed 12 weeks of treatment.

For efficacy, the interim analyses will include all data up to the cut-off date for the IA.

An analysis may be planned and reported separately on the relationship between measured plasma trough concentrations and trough FEV1 change from baseline as described in Section 2.10.

2.14 Additional analyses to assess the impact of COVID-19 pandemic

Number and percentage of patients enrolled (informed consent signed), discontinued double-blind treatment, completed double-blind treatment and exposed to double-blind treatment during the pre-COVID-19 pandemic period, the COVID-19 pandemic period and the post-COVID-19 pandemic period (if applicable) will be summarized by region and country using the FAS.

The pandemic periods are defined based on the start and end date of the pandemic in the respective region/country.

Demographics, baseline disease characteristics, and run-in spirometry will be summarized by time of enrollment (patients enrolled pre-COVID-19 pandemic, during COVID-19 pandemic, post-COVID-19 pandemic [if applicable]) to assess the impact of the COVID-19 pandemic on the study population.

Number and percentage of patients with COVID-19 related deviations will be summarized by deviation term and relationship to the COVID-19 pandemic. The PD process was used to identify COVID-19 related deviations even though these deviations were not true PDs.

To assess the impact of the COVID-19 pandemic on trough FEV1, the MMRM will be repeated for the following subgroups:

- by region (Latin and South America, Eastern Europe, Western Europe, Asia and Australia, North America)
- by time of enrollment (patients enrolled pre-COVID-19 pandemic, patients enrolled during COVID-19 pandemic)

The supplementary estimand considers differences between COVID-19 pandemic related and other discontinuations assuming missings related to COVID-19 pandemic are MAR.

To assess the impact of COVID-19 on safety, and to assess possible regional differences in reporting of AEs, the 10 most frequent AEs (in total) will be summarized by preferred term and region.

3 Sample size calculation

A total of 956 patients will be randomized to one of the 6 groups including 5 QBW251 dose groups (450, 300, 150, 75, 25 mg b.i.d.) and placebo. This includes the ~102 patients

randomized to the 450 mg b.i.d. arm prior to its discontinuation. Prior to the discontinuation of 450mg b.i.d., patients were randomized to QBW251 450, 300, 150, 75, 25 mg b.i.d., or placebo with an allocation ratio of 2:2:1:1:1:2. After discontinuation of 450mg b.i.d., patients were randomized to QBW251 300, 150, 75, 25 mg b.i.d., or placebo with an allocation ratio of 2:1:1:1:2. This sample size of 854 (956 total minus approximately 102 patients already randomized to 450 mg b.i.d.) achieves at least 80% power for dose-response signal detection on key endpoints for all models from the candidate set based on the MCP-Mod methodology and also to ensure an acceptable precision for the DR curve estimation. The calculations in [Table 3-1](#) exclude 450 mg b.i.d. from the analysis and are based on a 20% dropout rate, a one-sided significance level of 5%, and the following standard deviation assumptions.

- Pre-dose trough FEV₁: A common standard deviation of 200 mL based on previous Novartis COPD studies.
- E-RS Cough & Sputum weekly mean score: A common standard deviation of 1.3 based on the FLAME study ([Wedzicha et al 2016](#)).

Table 3-1 Power and Precision

Variable	Maximum improvement over placebo	Power to detect a DR signal	Average half-length of 90% confidence interval	
			Estimated DR curve	Estimated placebo-adjusted DR curve
Trough FEV ₁	60 mL	92%	21 mL	26 mL
	50 mL	81%		
E-RS Cough & Sputum	0.35	86%	0.14	0.17
	0.30	76%		

Power calculations were performed using ADDPLAN-DF-4.0 and the precision estimates (half-length of confidence interval) were obtained from simulations.

The randomization ratio was generally based on D-optimality criteria, which maximize the information on the dose-response curve, for the MCP-Mod analysis. The D-optimal allocation ratio randomizes approximately twice as many patients to placebo and the highest dose, compared to the middle doses.

4 Change to protocol specified analyses

Analysis of the primary endpoint:

Due to termination of the 450 mg b.i.d. arm, candidate curves E_{max}(ED₅₀=300), SigE_{max}(ED₅₀=300) and Exponential(delta=300) may no longer be appropriate for MCP-Mod analyses that do not include the 450 mg b.i.d. arm. These candidate curves will be removed and the Exponential(delta=75) will be added.

5 Appendix

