1.1 Study design

[figure not shown]
This study uses a 6 treatment arm, parallel-group, randomized, double-blind study design. One treatment arm (450 mg b.i.d.) was discontinued after reaching a pre-defined stopping criterion (see Section 12.7.1 of the protocol) at the first DMC interim analysis.

Patients initially undergo a screening period of 1 week. This screening period (Weeks -3 to -2) serves to assess eligibility and to taper patients off disallowed medications. Subsequently, patients enter the run-in period (2 weeks; Days -14 to 1) to establish baseline values for symptom assessments, to standardize the COPD background therapy (triple combination LABA/LAMA/ICS), and to complete eligibility assessments. At visit Run-In 2 final eligibility will be assessed. Eligible patients will move into the Day 1 visit where they will be randomized. Day 1 also generates additional baseline data and study treatment is initiated. The treatment period consists of 24 weeks, during which the patient returns to the site for regular visits (Day 1 – Week 24). Upon completion of the treatment period, patients are followed up for safety assessments during the Follow-Up period (Weeks 25 – 28).

Approximately 956 male and female COPD patients are randomized into 1 of 6 treatment arms with a randomization ratio of 2:2:1:1:1:2 (450 mg b.i.d. (discontinued), 300 mg b.i.d., 150 mg b.i.d., 75 mg b.i.d., 25 mg b.i.d., placebo). Detailed information regarding sample size calculation is provided in [Section 3](#). After reaching the pre-defined exposure-based stopping criterion, patients were no longer randomized to the 450 mg b.i.d. treatment, resulting effectively in a 2:1:1:1:2 randomization ratio (300 mg b.i.d.:150 mg b.i.d.: 75 mg b.i.d.: 25 mg b.i.d.: placebo) from the day of 450 mg b.i.d. discontinuation (20-Apr-2020) onward.

Randomization will be stratified by smoking status (current or ex-smoker) and severity of airflow limitation (FEV₁ \geq 30% to $<$ 50% and \geq 50% to $<$ 80%).

Figure 1-1 Study design

The primary endpoint will be assessed after 12 weeks of treatment.

Interim analyses (IA) on safety data are planned for an independent external safety data monitoring committee (DMC) to evaluate the results of pre-specified interim PK and safety data. Up to 5 DMC IAs are proposed to occur. Detailed information regarding DMC analysis will be provided in the DMC charter and a separate DMC SAP.

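### SAP 2.14 has no pandemic-period split of adverse events, and its enrolment-date FEV1 subgroup precedes the Week 12 measurement by 15 weeks, which dilutes the pre/during contrast

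*SAP*

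**What the plan says.** SAP 2.14 states its FEV1 aim and method together: "To assess the impact of the COVID-19 pandemic on trough FEV1, the MMRM will be repeated for the following subgroups". There are two subgroupings. One is "by region (Latin and South America, Eastern Europe, Western Europe, Asia and Australia, North America"). The other is "by time of enrollment (patients enrolled pre-COVID-19 pandemic, patients enrolled during COVID-19 pandemic"). Enrolment means consent: the Protocol glossary defines it so, and SAP 2.14 repeats it in its disposition summary ("Number and percentage of patients enrolled (informed consent signed), discontinued double-blind treatment, completed double-blind treatment and exposed to double-blind treatment").

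For safety, the section names two aims, the impact of COVID-19 and possible regional differences in adverse event reporting. One table serves both: "the 10 most frequent AEs (in total) will be summarized by preferred term and region".

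The periods are local: "The pandemic periods are defined based on the start and end date of the pandemic in the respective region/country". No calendar dates are given. The disposition and exposure counts are tabulated by pre-, during- and post-pandemic period. Demographics, baseline disease characteristics and run-in spirometry are summarised by time of enrolment, with a post-pandemic category if needed; the FEV1 subgroup has no such category. On missing data the section adds: "The supplementary estimand considers differences between COVID-19 pandemic related and other discontinuations assuming missings related to COVID-19 pandemic are MAR".

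**The concern.** A pandemic can act on an outcome through the calendar time at which that outcome is measured or reported. Consent date is a sensible classifier for demographics and run-in spirometry, which are collected within about two weeks of consent. It fits less well for an endpoint due 15 weeks later. Patients who consented shortly before the local start sit in the pre-pandemic group with a Week 12 value from the pandemic. This pulls the two groups together and biases the comparison towards finding no difference.

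The safety table has a simpler gap. With no before/during split, a high count in one region could reflect the pandemic there, ordinary reporting habits or case mix, and nothing in the table distinguishes these. What is at stake is how far 2.14 can support a statement in the study report that the pandemic did or did not matter for FEV1 and safety.

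**Working it through.** **Inputs.** Consent is at Screening, Day -21; Week 12 is Day 85, Week 24 is Day 169 and Follow-Up is Day 197 (Protocol Table 8-1). The SAP agrees on the lead-in: "Patients initially undergo a screening period of 1 week", followed by a two-week run-in. Study day has no Day 0 (SAP 2.1.1.1), so Day -21 is 21 days before first dose and Day 85 is 84 days after it.

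**Check against the plan's own figure.** Consent to Follow-Up: 21 + 196 = 217 days; 217 / 7 = 31.0 weeks. The Protocol summary gives 31 weeks, so the day count is right.

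**Lag.**
- Consent to Week 12: 21 + 84 = 105 days = 15 weeks.
- Consent to Week 24: 21 + 168 = 189 days = 27 weeks.

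**Share misclassified at Week 12.** Suppose local enrolment ran evenly for T weeks before the local pandemic start, and the pandemic period lasted at least 15 weeks. The share of the pre-pandemic group whose Week 12 visit falls in the pandemic is m = min(1, 15/T). If the true difference between periods is d and depends only on the date of the Week 12 visit, the expected observed difference is d − m·d = (1 − m)·d.

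| T (weeks, assumed) | m | contrast retained, 1 − m |
|---|---|---|
| 15 or less | 100% | 0% |
| 20 | 75% | 25% |
| 26 | 58% | 42% |
| 39 | 38% | 62% |
| 52 | 29% | 71% |

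**Adverse events.** No arithmetic is needed to see that a table by preferred term and region has no pandemic contrast. Splitting it by consent date would not help much, because follow-up runs to about 31 weeks after consent. The share of pre-pandemic consenters with some time on study during the pandemic is min(1, 31/T): 100% at T = 26, 79% at T = 39 and 60% at T = 52. Event onset date is the classifier that fits.

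**Is it covered elsewhere?** The period summaries in SAP 2.14 count patients enrolled, discontinued, completed and exposed, but not FEV1 values or events. The supplementary estimand (SAP 2.5.4 and 5.7.1) deals with COVID-19 related discontinuation and missing values, not with FEV1 values observed during the pandemic. Exposure-adjusted event rates are planned in SAP 2.8.1, by treatment but not by period.

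**The case against.** The strongest objection concerns the endpoint. It is change from baseline, and under the enrolment split every patient in the during group has both baseline and Week 12 after the local start. Re-cutting by Week 12 date alone would bring patients with a pre-pandemic baseline into that group, so the mixing would only move. The MMRM also covers Weeks 4 to 24, so one cut at Week 12 cannot suit every visit. This stands, and it is why the enrolment split should be supplemented and not replaced.

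Several further points also stand:
- The region table does serve the section's second safety aim.
- Disposition and exposure already use calendar periods, so it would be wrong to infer that 2.14 as a whole ignores calendar time.
- Each dose is compared with concurrently randomised placebo, and no decision rule uses these subgroups.
- The dilution figures assume a step effect at the Week 12 date and an enrolment length that the documents do not give.

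A reader might infer that the FEV1 subgroup cannot show any pandemic effect. The documents do not support that. Patients who consented more than 15 weeks before the local start have Week 12 before it, so a contrast remains unless enrolment was shorter than that.

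A reader might also infer a large affected group from the roughly 102 patients on 450 mg: 102 × 9/2 = 459 randomised by 20-Apr-2020. That date is when the arm stopped, not a pandemic date. Some of the 459 may already belong to the during group, and about 102 are on 450 mg and excluded from the model, leaving about 357. The size of the pre-pandemic group cannot be derived from the documents.

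**Conclusion.** The point holds as two limited weaknesses in additional analyses. First, the adverse event table cannot serve its stated COVID-19 aim, because it has no period split; this depends on no assumption. Second, the enrolment-date FEV1 subgroup misplaces, at Week 12, patients who consented up to 15 weeks before the local start. The lag of 105 days follows from the visit schedule. The resulting dilution of 58%, 38% or 29% rests on assumed even enrolment over 26, 39 or 52 weeks, a local pandemic period of at least 15 weeks, and an effect tied to the visit date. The primary analysis is untouched, and the change is a cheap improvement, not a condition for the validity of the trial.

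**What to change.** **Safety.** Keep the region table. Add adverse events by onset before or during (and after, if applicable) the local pandemic period, with exposure-adjusted rates within region. Show them by treatment group, since the mix of arms contributing follow-up changes once the 450 mg arm stops. Event start dates are collected (Protocol 10.1.1), the local period dates are already needed for SAP 2.14, and patient-time in each period follows from the dosing dates.

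**FEV1.** Keep the enrolment-date subgroup. Add a grouping by planned Day 1 and planned Week 12 date (randomisation + 84 days) relative to the local start: both before, straddling, both during. Planned dates are fixed at randomisation, so the grouping introduces no post-randomisation selection, and a separate straddling group avoids mixing either of the others at the start date. State how patients whose Week 12 falls after the local pandemic end are classed.

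**Cost.** A few sentences in SAP 2.14 and a little more programming from dates already held. The subgroups will be smaller and their estimates less precise, so the results should be read as descriptive.
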